7.2.1.5 FOLFIRI

Dose delays and treatment restarts will be made at the discretion of the site investigator according to institutional guidelines or local standard practice. The recommended dose reduction is stepwise by 20%. Discontinuation of treatment should be considered if dose reduction below the following dosage is required: Irinotecan 120 mg/m² and 5-FU infusion 1600 mg/m² 46 to 48 hours.

7.3 Method of Treatment Assignment

Treatment allocation will be accomplished by non-random assignment. There are 5 planned treatment cohorts in Part 1 (dose finding) and Part 2 (dose confirmation). This is an open-

label trial. Treatment allocation will be accomplished by non-random assignment. If a participant meets the eligibility criteria for Cohorts B and C (ie, previously untreated) or Cohorts D and E (ie, previously treated with one line of fluoropyrimidine-based therapy), then IVRS/IWRS will alternate assignments between the 2 cohorts with the same eligibility criteria. Treatment for each cohort in Part 2 will begin once a preliminary RP2D for that cohort is identified in Part 1.

7.3.1 Stratification

No stratification based on age, sex or other characteristics will be used in this trial.

7.4 Blinding

This is an open-label trial; therefore, the Sponsor, investigator and participant will know the study drug administered.

7.5 Preparation/Handling/Storage/Accountability

7.5.1 Dose Preparation

The rationale for selection of doses to be used in this trial is provided in Section 3.2 – Background.

7.5.1.1 Pembrolizumab

The Pharmacy Manual contains specific instructions for preparation of the pembrolizumab infusion fluid and administration.

7.5.1.2 Binimetinib

Binimetinib is an oral medication, and it is supplied as film-coated tablets in dosage strength of 15 mg. There are no specific calculations or evaluations required to be performed in order to administer the proper dose to each participant.

7.5.1.3 Standard of Care Chemotherapies (mFOLFOX7 and FOLFIRI)

Preparation of SOC chemotherapies must follow local standards.

7.5.2 Handling, Storage and Accountability

The investigator or designee must confirm appropriate temperature conditions have been maintained during transit for all study treatment received and any discrepancies are reported and resolved before use of the study treatment.

Only participants enrolled in the study may receive study treatment and only authorized site staff may supply or administer study treatment. All study treatments must be stored in a secure, environmentally controlled, and monitored (manual or automated) area in accordance with the labeled storage conditions with access limited to the investigator and authorized site staff.

The investigator, institution, or the head of the medical institution (where applicable) is responsible for study treatment accountability, reconciliation, and record maintenance (ie, receipt, reconciliation, and final disposition records).

For all trial sites, the local country Sponsor personnel or designee will provide appropriate documentation that must be completed for drug accountability and return, or local discard and destruction if appropriate. Where local discard and destruction is appropriate, the investigator is responsible for ensuring that a local discard/destruction procedure is documented.

The trial site is responsible for recording the lot number, manufacturer, and expiry date for any locally purchased product as per local guidelines unless otherwise instructed by the Sponsor.

The investigator shall take responsibility for and shall take all steps to maintain appropriate records and ensure appropriate supply, storage, handling, distribution and usage of study treatments in accordance with the protocol and any applicable laws and regulations.

7.6 Treatment Compliance

Pembrolizumab and SOC chemotherapies will be administered by the investigator and/or study staff according to the specifications within the pharmacy manual. The total volume of study medication infused will be compared with the total volume prepared to determine compliance with each dose administered.

Participants receiving binimetinib should be instructed to bring their study drug supply and bottles, to the site at each study visit. Compliance will be evaluated at each visit by review of an accounting of returned study drug.

Interruptions from the protocol specified treatment plan for ≥ 12 weeks require consultation between the investigator and the Sponsor and written documentation of the collaborative decision on participant management.

7.7 Concomitant Therapy

If a participant does not discontinue all prior medications within 14 days of the first dose of study treatment, he/she may be included in the study if the investigator can rationalize that the specific use of a prior medication is not clinically relevant within the context of the trial.

Concurrent use of any prescription or non-prescription medication, or concurrent vaccination, during the course of the trial (ie, after randomization or treatment allocation) must first be discussed between the investigator and Sponsor prior to administration, unless appropriate medical care necessitates that therapy or vaccination should begin before the investigator and Sponsor can consult. The participant will be allowed to continue in the trial if both the Sponsor and the investigator agree.

Listed below are specific restrictions for concomitant therapy during the course of the trial: Participants are prohibited from receiving the following therapies during the Screening and Treatment Phases (including retreatment for post- CR relapse) of this trial: Participants who, in the assessment of the investigator, require the use of any of the treatments mention for

clinical management should be discontinued from treatment. Participants may receive other medications that the investigator deems to be medically necessary.

- Antineoplastic systemic chemotherapy or biological therapy not specified in this study
- Immunotherapy not specified in this protocol
- Chemotherapy not specified in this protocol
- Investigational agents other than pembrolizumab and binimetinib
- Radiation therapy

Note: Radiation therapy to a symptomatic solitary lesion or to the brain may be allowed at the investigator's discretion.

- Live vaccines within 30 days prior to the first dose of trial treatment and while participating in the trial. Examples of live vaccines include, but are not limited to, the following: measles, mumps, rubella, varicella/zoster, yellow fever, rabies, BCG, and typhoid vaccine. Seasonal influenza vaccines for injection are generally killed virus vaccines and are allowed; however, intranasal influenza vaccines (eg, FluMist®) are live attenuated vaccines and are not allowed.
- Systemic glucocorticoids for any purpose other than to modulate symptoms from an ECI that is suspected to have an immunologic etiology. The use of physiologic doses of corticosteroids may be approved after consultation with the Sponsor.
- Glucocorticoids (inhaled steroids as part of a stable regimen for the treatment of asthma/ COPD are permitted) for any purpose other than to modulate symptoms from an AE. The use of physiologic doses of corticosteroids may be approved after consultation with the Sponsor. Additionally, a short limited course of steroids may be used to treat medical conditions and/or AEs during the study after sponsor notification and consultation.

Note: Use of prophylactic corticosteroids to avoid allergic reactions (eg, IV contrast dye) and as a part of anti-emetic therapy for chemotherapy is permitted.

- Participants who, in the assessment of the investigator, require the use of any of the aforementioned treatments for clinical management should be removed from the trial. Participants may receive other medications that the investigator deems to be medically necessary.

Participants who, in the assessment of the investigator, require the use of any of the aforementioned treatments for clinical management should be removed from the study.

All treatments that the investigator considers necessary for a participant's welfare may be administered at the discretion of the investigator in keeping with the community standards of medical care. All concomitant medication will be recorded on the eCRF including all prescription, over-the-counter products, herbal supplements, and IV medications and fluids. If changes occur during the study period, documentation of drug dosage, frequency, route, and date should also be included on the eCRF.

All concomitant medications received within 28 days prior to the first dose of study treatment and up to 30 days after the last dose of study treatment should be recorded. Concomitant medications administered 30 days after the last dose of study treatment should be recorded for SAEs and ECIs as defined in Section 9.3.7.

Medications or vaccinations specifically prohibited in the exclusion criteria are not allowed during the ongoing study. If there is a clinical indication for any medication or vaccination specifically prohibited during the study, discontinuation from study therapy or vaccination may be required. The investigator should discuss any questions regarding this with the Sponsor. The final decision on any supportive therapy or vaccination rests with the investigator and/or the participant's primary physician. However, the decision to continue the participant on study treatment requires the mutual agreement of the investigator, the Sponsor and the participant.

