9.3.7 Events of Clinical Interest (ECI)

Selected non-serious and serious adverse events are also known as Events of Clinical Interest (ECI) and must be reported to the Sponsor.

Events of clinical interest for this trial include:

1. an overdose of Sponsor's product, as defined in Section 9.4 – Treatment of Overdose, that is not associated with clinical symptoms or abnormal laboratory results.
2. an elevated AST or ALT lab value that is greater than or equal to 3X the upper limit of normal and an elevated total bilirubin lab value that is greater than or equal to 2X the upper limit of normal and, at the same time, an alkaline phosphatase lab value that is less than 2X the upper limit of normal, as determined by way of protocol-specified laboratory testing or unscheduled laboratory testing.*

*Note: These criteria are based upon available regulatory guidance documents. The purpose of the criteria is to specify a threshold of abnormal hepatic tests that may require an additional evaluation for an underlying etiology. The trial site guidance for assessment and follow up of these criteria can be found in the Investigator Trial File Binder (or equivalent).

For the time period beginning when the consent form is signed until treatment allocation/randomization, any ECI, or follow up to an ECI, that occurs to any participant must be reported within 24 hours to the Sponsor if it causes the participant to be excluded from the trial, or is the result of a protocol-specified intervention, including but not limited to washout or discontinuation of usual therapy, diet, placebo treatment or a procedure.

For the time period beginning at treatment allocation/randomization through 30 days following cessation of treatment, any ECI, or follow up to an ECI, whether or not related to the Sponsor's product, must be reported within 24 hours to the Sponsor, either by electronic media or paper. Electronic reporting procedures can be found in the EDC data entry

guidelines. Paper reporting procedures can be found in the Investigator Trial File Binder (or equivalent).

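### Section 7.7 has two glucocorticoid prohibitions with different exceptions, and the narrower one bars steroids that Table 6 directs while pembrolizumab is only withheld

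*Combined protocol and SAP*

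**What the plan says.** Among the therapies prohibited during screening and treatment, Section 7.7 lists "Systemic glucocorticoids for any purpose other than to modulate symptoms from an ECI that is suspected to have an immunologic etiology", with physiologic doses possible after consulting the Sponsor. The bullet directly after it prohibits glucocorticoids "for any purpose other than to modulate symptoms from an AE" and adds that "a short limited course of steroids may be used to treat medical conditions and/or AEs during the study after sponsor notification and consultation". Both bullets are current text, and no sentence says which prevails.

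Three sentences in the same section attach a consequence to needing a listed therapy. The lead-in says that participants who require one for "clinical management should be discontinued from treatment". The last bullet says they should be removed from the trial. The sentence after the list says that those who "require the use of any of the aforementioned treatments for clinical management should be removed from the study".

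For the meaning of ECI, Section 7.7 has its own pointer: later concomitant medications "should be recorded for SAEs and ECIs as defined in Section 9.3.7". Section 9.3.7 then names two items. The first is an overdose "that is not associated with clinical symptoms or abnormal laboratory results". The second is AST or ALT at or above 3 times ULN with total bilirubin at or above 2 times ULN and, "at the same time, an alkaline phosphatase lab value that is less than 2X the upper limit of normal".

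**The concern.** The two bullets give opposite answers for the same use of the same drug class. Because both are prohibitions, satisfying the exception in one does not lift the other. The narrower bullet rests on a defined term that leaves out most of the immune-related events for which the protocol itself directs steroids.

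At stake is the handling of a participant with a manageable immune-related event. Table 6 would pause pembrolizumab, treat and taper. A site that applies the first bullet literally, together with the consequence sentences, could stop treatment or take the participant off study, or could hesitate over steroids. Removal from the study is the heavier outcome. Section 8.1 keeps participants who stop treatment under observation, whereas Section 8.2 ends scheduled visits for those who withdraw.

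**Working it through.** No arithmetic bears on this point, so the check sets the provisions side by side.

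**Step 1: which ECIs could justify steroids?** The overdose item is by definition free of symptoms, so there is nothing to modulate. That leaves the liver pattern, which needs all three laboratory conditions at once. Section 9.3.7 introduces its list with an open verb (*include*), and Table 10 refers to ECIs other than potential DILI, but no further ECI is named anywhere.

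**Step 2: apply both bullets to the Table 6 rows that give a stated steroid dose while pembrolizumab is only withheld.**

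| Event | Table 6 starting dose (prednisone or equivalent) | Named ECI? | First bullet | Second bullet |
|---|---|---|---|---|
| Pneumonitis, Grade 2 | 1-2 mg/kg | No | Prohibited | Allowed |
| Diarrhea/colitis, Grade 2 or 3 | 1-2 mg/kg | No | Prohibited | Allowed |
| Nephritis, Grade 2 | 1-2 mg/kg | No | Prohibited | Allowed |
| AST/ALT or bilirubin, Grade 2 | 0.5-1 mg/kg | Only if all three laboratory criteria are met | Prohibited otherwise | Allowed |

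On the last row, Table 7 puts Grade 2 AST/ALT at more than 3 and up to 5 times ULN. It has a separate entry for such cases with bilirubin no higher than 2 times ULN, so the protocol expects transaminase elevations outside the ECI pattern.

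The other six of the ten Table 6 rows add less. Grade 1 myocarditis and other persistent Grade 2 events get steroids according to severity, with pembrolizumab withheld. Hypophysitis may fall under the physiologic-dose allowance. The diabetes/hyperglycemia, hyperthyroidism and hypothyroidism rows use no steroid.

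**Step 3: does the physiologic-dose allowance rescue the first bullet?** Not for the four rows above. Exclusion criterion 9 in Section 6.2 uses that term for replacement in adrenal or pituitary insufficiency, not for a treatment course at these doses.

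**Step 4: compare the consequence sentences with the rest of the protocol.**

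- Table 6 withholds pembrolizumab for these events and does not stop it.
- Sections 3.3.1.2 and 3.3.1.3 make systemic corticosteroids mandatory for suspected autoimmune hepatitis and immune-related colitis. Sections 3.3.1.1 and 7.2.1.1 call early steroids critical.
- Section 8.1 lists the reasons for mandatory discontinuation. Recurrent Grade 2 pneumonitis is there; a first episode is not, and neither is steroid use.
- Section 8.2 requires withdrawal from the study only when consent is withdrawn.
- Section 7.7 itself says that a participant may continue if Sponsor and investigator agree. It also says that an indicated but prohibited medication makes discontinuation a possibility, to be discussed with the Sponsor.

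The first bullet and the consequence sentences therefore conflict with Table 6, with Section 8.1 and with other paragraphs of Section 7.7.

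**The case against.** The best defence is that the protocol, read as a whole, leaves little doubt about what was meant. The second bullet, Table 6, Section 7.7.1 and Section 9.3.8 all support steroids for immune-related events. Section 7.7 allows urgent therapy before the Sponsor can be consulted, leaves treatments needed for a participant's welfare to the investigator, and gives the final say on supportive therapy to the investigator and/or the primary physician. A site would have to set many specific directions aside to follow one bullet. The ECI list is also not strictly closed.

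Most of this stands, and it limits the consequence. It does not remove the conflict. None of these clauses deletes the first bullet or the consequence sentences, and they leave the site to reconcile contradictory instructions while managing an acute toxicity. If the ECI list is open, the bullet's scope becomes uncertain, which does not make it correct.

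Three stronger readings are tempting, and the documents do not support them:

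- A reader might infer that every participant given Table 6 steroids must be removed. The continuation route in Section 7.7 and the lists in Sections 8.1 and 8.2 rule that out.
- A reader might infer a distorted DLT count, since Section 5.1.3 counts a treatment-related toxicity that causes discontinuation during the DLT period. But Section 5.1.4 keeps a participant evaluable when a prohibited medication treats a drug-related AE, and nothing forces the discontinuation.
- A reader might multiply the pooled 3.4% pneumonitis rate in Section 3.3.1.1 by the planned enrolment. That rate covers all grades, including Grade 1, which has no Table 6 row, and Grades 3 and 4, which are permanently discontinued anyway. Rates for these combinations are not given, and how often a site would follow the first bullet is unknown.

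**Conclusion.** The inconsistency is real and worth correcting. As written, the ECI-only bullet classes as prohibited a set of steroid treatments that the toxicity plan directs, and the attached sentences point to discontinuation or removal where Table 6 only withholds pembrolizumab. This rests on taking the ECI definition from Section 9.3.7, as Section 7.7 does, and on reading physiologic doses as replacement therapy.

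The practical size is modest. The intent is recoverable and Sponsor consultation is built in, so what remains is inconsistent handling between sites, an occasional unneeded discontinuation, or hesitation over steroids. The number affected is likely to be small, but the documents give no basis for estimating it. No effect on DLT rates, the RP2D or any planned analysis is shown.

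**What to change.** Delete the ECI-only bullet, or change ECI to AE in it and merge the two bullets. Add one sentence to Section 7.7: corticosteroids given under Table 6, Table 8 or Section 7.7.1 and its subsections are not prohibited therapy and do not trigger the discontinuation or removal sentences.

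Two minor editorial points could go into the same amendment. The anti-emetic note in Section 7.7 covers prophylactic steroids only with chemotherapy, although Section 7.7.1.2 suggests prophylactic dexamethasone with binimetinib and Cohort A receives no chemotherapy. Section 7.2.1.2 sends the reader to Section 7.7.1.4, the FOLFIRI guidance, for corticosteroid use; Section 7.7.1 is the right target.

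The cost is amendment wording only, with no new procedure and no change to the DLT definition or any endpoint.

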7.7.1 Rescue Medications & Supportive Care

For adverse events included in the protocol, if the investigator cannot definitively attribute to any particular component of the regimen, supportive care including steroid use should follow general recommendations below.

Participants should receive appropriate supportive care measures as deemed necessary by the treating investigator. Suggested supportive care measures for the management of AEs with potential immunologic etiology are outlined along with the dose modification guidelines in Section 7.2 and [Table 6](#). Where appropriate, these guidelines include the use of oral or IV treatment with corticosteroids, as well as additional anti-inflammatory agents if symptoms do not improve with administration of corticosteroids. Note that several courses of steroid tapering may be necessary as symptoms may worsen when the steroid dose is decreased. For each disorder, attempts should be made to rule out other causes such as metastatic disease or bacterial or viral infection, which might require additional supportive care. The treatment guidelines are intended to be applied when the investigator determines the events to be related to pembrolizumab.

Note: If after the evaluation of the event, it is determined not to be related to pembrolizumab, the investigator does not need to follow the treatment guidance. Refer to [Table 8](#) in Section 7.7.1.1 for guidelines regarding dose modification and supportive care.

It may be necessary to perform conditional procedures such as bronchoscopy, endoscopy, or skin photography as part of evaluation of the event.

7.7.1.1 Supportive Care Guidelines for Pembrolizumab

Dose Modification and Toxicity Management of Infusion-Reactions Related to Pembrolizumab

Pembrolizumab may cause severe or life threatening infusion-reactions including severe hypersensitivity or anaphylaxis. Signs and symptoms usually develop during or shortly after drug infusion and generally resolve completely within 24 hours of completion of infusion. Dose modification and toxicity management guidelines on pembrolizumab associated infusion reaction are provided in [Table 8](#).

Table 8 Pembrolizumab Infusion Reaction Dose Modification and Treatment Guidelines

NCI CTCAE Grade	Treatment	Premedication at Subsequent Dosing
Grade 1 Mild reaction; infusion interruption not indicated; intervention not indicated	Increase monitoring of vital signs as medically indicated until the participant is deemed medically stable in the opinion of the investigator.	None
Grade 2 Requires therapy or infusion interruption but responds promptly to symptomatic treatment (eg, antihistamines, NSAIDs, narcotics, IV fluids); prophylactic medications indicated for ≤ 24 hrs	
Stop Infusion.
 
Additional appropriate medical therapy may include but is not limited to:
 
IV fluids Antihistamines NSAIDs Acetaminophen Narcotics
 
Increase monitoring of vital signs as medically indicated until the participant is deemed medically stable in the opinion of the investigator. If symptoms resolve within 1 hour of stopping drug infusion, the infusion may be restarted at 50% of the original infusion rate (eg, from 100 mL/hr to 50 mL/hr). Otherwise dosing will be held until symptoms resolve and the participant should be premedicated for the next scheduled dose.
 
Participants who develop Grade 2 toxicity despite adequate premedication should be permanently discontinued from further treatment with pembrolizumab
	Participant may be premedicated 1.5 h (\pm 30 minutes) prior to infusion of pembrolizumab with: Diphenhydramine 50 mg po (or equivalent dose of antihistamine). Acetaminophen 500-1000 mg po (or equivalent dose of analgesic).
Grades 3 or 4 Grade 3: Prolonged (ie, not rapidly responsive to symptomatic medication and/or brief interruption of infusion); recurrence of symptoms following initial improvement; hospitalization indicated for other clinical sequelae (eg, renal impairment, pulmonary infiltrates) Grade 4: Life-threatening; pressor or ventilatory support indicated	
Stop Infusion.
 
Additional appropriate medical therapy may include but is not limited to:
 
Epinephrine** IV fluids Antihistamines NSAIDs Acetaminophen Narcotics Oxygen Pressors Corticosteroids
 
Increase monitoring of vital signs as medically indicated until the participant is deemed medically stable in the opinion of the investigator. Hospitalization may be indicated.
 
**In cases of anaphylaxis, epinephrine should be used immediately.
 
Participant is permanently discontinued from further treatment with pembrolizumab.
	No subsequent dosing
Appropriate resuscitation equipment should be available at the bedside and a physician readily available during the period of drug administration. For further information, please refer to the Common Terminology Criteria for Adverse Events v4.0 (CTCAE) at http://ctep.cancer.gov		

Other allowed dose interruption for pembrolizumab

Pembrolizumab may be interrupted for situations other than treatment-related AEs such as medical / surgical events or logistical reasons not related to study therapy. Participants should be placed back on study therapy within 3 weeks of the scheduled interruption, unless otherwise discussed with the Sponsor. The reason for interruption should be documented in the patient's study record.

